9.3.2 Outcomes definition

The study outcomes will be defined based on Read codes and ICD-9/10-CM diagnosis and procedure codes or laboratory, vital sign and other patient observation results.

Algorithms for the definition of recurrent VTE and of the bleeding events have previously been developed and refined using all information available in CPRD, HES and Office of National Statistics ONS [4, 8].

A random sample of identified potential VTE recurrences and significant bleeding events will be manually reviewed by utilizing patient summaries/profiles including HES APC, HES Outpatient, ONS death registration data (DRD) and PCP recorded symptoms, signs, laboratory tests, diagnostic and therapeutic procedures, medication use, discharge diagnoses, and cause of death to confirm the that outcomes have been appropriately identified.

Primary outcomes

- The risk of recurrent VTE at 3-months
- Composite of any major bleeding or clinically-relevant non-major bleeding-related hospitalization (per the ISTH criteria [9, 10] for identification of bleeding-associated hospitalizations) at 3-months
- All-cause mortality at 3-months

Secondary outcomes

- Recurrent VTE at 6- and 12-months post-index VTE

- Composite of any major or clinically-relevant nonmajor bleeding-related hospitalization at 6- and 12-months post-index VTE, including:
 - Intracranial hemorrhage (ICH)
 - Critical organ bleeding (e.g., intracranial, intraspinal, intraocular, retroperitoneal, intraarticular or pericardial bleeding or intramuscular with compartment syndrome)
 - Extracranial bleeding-related hospitalizations (including trauma-related)
- Composite of any major bleeding or clinically-relevant non-major bleeding-related hospitalization (per the ISTH criteria [9, 10] for identification of bleeding-associated hospitalizations) at 6 and 12-months
- Intracranial hemorrhage (ICH), critical organ bleeding and extracranial bleeding-related hospitalizations as separate outcomes
- All-cause mortality at 6- and 12-months
- Incidence rates of recurrent VTE, any clinically-relevant bleeding-related hospitalization and all cause-mortality in rivaroxaban, DOAC and LMWH patients experiencing CAT regardless of the bleeding risk associated with cancer type
- Duration of anticoagulation treatment and rivaroxaban, DOAC and LMWH discontinuation rates at 3-, 6-, 12-months and all available follow-up

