9.5 Study size

Based on an incidence rate of VTE of 131.5 per 100,000 person-years and assuming that 18.6% of VTEs are associated with active cancer (1) and that 50% of patients with CAT have a recording for DOACs or LMWH within 30 days after initial VTE, we expect our cohort to include approximately 5,600 patients with CAT. Assuming a mean follow-up of 0.6 years following first CAT (according to the high mortality risk in these patients and the restriction to the first year following CAT) and incidence rates of 11.8 VTE recurrences, 14.4 significant bleeds and 80.0 deaths from any cause per 100 person-years, we expect to identify approximately 390 VTE recurrences, 480 significant bleeds and 2670 deaths from any cause within the first year after CAT. Based on the matching related fixed proportion of DOAC to LMWH users in our study cohort and the numbers mentioned above, this study would detect a significant difference between DOAC and LMWH users with 5% significance level and a power of 80% if the estimated HR is lower than 0.75, 0.77 or 0.89 respectively for VTE recurrence, serious bleeding or death from any cause. This is consistent with the HR of recurrent VTE ≤ 0.43 (supported by SELECT-D [14] and Costa et al. [15]) or with a more conservative HR (HR=0.71) as seen in the Hokusai VTE cancer trial for edoxaban (DOAC) compared to dalteparin (LMWH) [16].

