9.7 Data analysis

Baseline characteristics will be analyzed using descriptive statistics. Categorical data will be reported as percentages and continuous data as medians with accompanying 25%, 75% ranges or means \pm standard deviations (SDs). Descriptive analysis will be performed for each of the three distinct cancer cohorts listed above, namely, (1) the cohort of cancer patients without gastrointestinal and genitourinary cancers, (2) the cohort defined by the ISTH CAT guidelines (in acute CAT patients without a malignant neoplasm associated with a high risk of bleeding) and (3) an all cancer type cohort.

To adjust for potential confounding between the rivaroxaban (or DOAC) and LMWH cohorts, propensity scores will be calculated using a multivariable logistic regression model. The propensity score model will include commonly used variables and accepted risk factors for differential anticoagulation exposure identified at baseline including demographics, comorbidities, laboratory values, vital signs, other clinical observations and outpatient medication use (prescription and over-the-counter). All clinical characteristics listed in section 9.3.3 of this protocol will be included in the propensity score model. Propensity scores will then be used to assign weight to individual patients in the analysis using an overlap weighting approach. Overlap weighting assigns weights to patients that are proportional to their probability of belonging to the opposite treatment cohort. By design, overlap weighting results in the exact balance of all variables included in the propensity score model. This method of adjustment retains all patients in the dataset (unlike propensity score matching) and gives less weight to patients with extreme propensity scores (which is often a concern with inverse probability weighting).

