Cox proportional hazards regression is a method for investigating the effect of variables upon the time a specified event takes to happen. We will fit Cox proportional hazards regression models (with robust estimators) to compare event rates over time for the rivaroxaban (or any DOAC) and LMWH cohorts in the Xarelto SmPC and CAT guidance cancer type cohorts. As propensity score based methods will be assumed to

Reference Number: RD-SOP-1214
Supplement Version: 7

balance key characteristics of the treatment cohorts, the only independent variable that will be included into Cox regression model will be anticoagulant received (rivaroxaban or DOAC or LMWH). Results of Cox regression will be reported as hazard ratios (HRs) with 95% confidence intervals (CIs).

We will use an intention-to-treat approach to analyze the data in which, patients will be evaluated based on the initial anticoagulant prescription registered and will be followed until endpoint occurrence, end-of-database activity, end of data availability or end of designated follow-up time (3-, 6- or 12-months), whichever comes first. Time from treatment initiation to end of follow-up will then be considered the time at risk. On-treatment analysis (patients will be followed until endpoint occurrence, end-of-database activity, end of data availability, end of designated follow-up time (3-, 6- or 12-months), anticoagulant discontinuation or switch, whichever comes first) will be performed as a sensitivity analysis. No adjustments for multiple hypothesis testing will be performed.

Subgroup analyses

Analysis of the recurrent VTE, any clinically-relevant bleeding-related hospitalization and all-cause mortality outcomes among patients prescribed with rivaroxaban and any DOAC (apixaban, dabigatran, edoxaban, rivaroxaban) versus patients prescribed with LMWH patients for acute CAT will be performed stratifying by cancer subtypes (specific subtypes dependent on available sample sizes). To limit the number of analyses performed (and the impact of multiple hypothesis testing), subgroup analyses will only be performed on the primary effectiveness and safety endpoints (recurrent VTE, any clinically-relevant bleeding-related hospitalization and all-cause mortality).

Further descriptive analyses

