We will calculate incidence rates of recurrent VTE, any clinically-relevant bleeding-related hospitalization and all-cause mortality in rivaroxaban patients experiencing CAT regardless of the cancer type and associated bleeding risk. The duration of anticoagulation treatment and discontinuation rates at 3-, 6- and 12-months follow-up will be estimated based on instructions at prescriptions filled in CPRD.

Sensitivity analyses

Various sensitivity analyses will be performed to test the robustness of our study's conclusions. A sensitivity analysis will be performed whereby patients with cancer will need to be admitted to the hospital, emergency department or observation unit for acute DVT and/or PE on or after January 1, 2013 in order to better estimate the "contemporary" comparative effectiveness and safety of the two treatment cohorts/strategies. We will perform 1:1 propensity score matching of rivaroxaban and LMWH patients and

analyze data using a proportional hazards models for the subdistribution of competing risk (competing risk model) to compare event incidences over time for the cohorts. An “on-treatment” approach (patients censored at the first event, anticoagulant discontinuation or switch or end of data availability) will also be performed as the CPRD GOLD and Aurum EHR contain prescription instructions commonly used to identify continuous anticoagulation use. Analysis at 6 and 12-months will be performed.

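### The 3-month VTE risk named as a primary outcome is not estimated by the overlap-weighted Cox analysis, and the only competing-risk model is tied to 1:1 matching of rivaroxaban and LMWH patients

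*Protocol*

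**What the plan says.** Section 9.3.2 lists three primary outcomes at 3 months. The first is worded as "The risk of recurrent VTE at 3-months", the second is the bleeding composite, and the third is "All-cause mortality at 3-months". The same events at 6 and 12 months are secondary.

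Section 9.7 fixes the main adjustment: "Propensity scores will then be used to assign weight to individual patients in the analysis using an overlap weighting approach". It then fixes the model, "We will fit Cox proportional hazards regression models (with robust estimators) to compare event rates over time", and the output, "Results of Cox regression will be reported as hazard ratios (HRs) with 95% confidence intervals (CIs". Patients are "followed until endpoint occurrence, end-of-database activity, end of data availability or end of designated follow-up time (3-, 6- or 12-months), whichever comes first". Death is not named in that list. No cumulative incidence or comparative absolute risk is named anywhere. The only absolute measures are descriptive incidence rates in the cohort of all cancer types.

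Section 9.5 assumes "incidence rates of 11.8 VTE recurrences, 14.4 significant bleeds and 80.0 deaths from any cause per 100 person-years".

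Competing risks appear once, under Sensitivity analyses in section 9.7. A single sentence plans 1:1 propensity-score matching of rivaroxaban and LMWH patients and then says the team will "analyze data using a proportional hazards models for the subdistribution of competing risk (competing risk model". Matching is also listed without that model, as one example of a sensitivity analysis, in the section 9.7 discussion of weighting methods. The Abstract mentions it too.

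**The concern.** Where death is much more frequent than the event of interest, the hazard ratio for the event and the ratio or difference of its risks answer different questions. The hazard ratio compares event rates among patients still alive and event-free. The risk also depends on how many patients die first. The protocol names a risk for VTE, but its main analysis produces only the rate comparison.

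The analysis that would address this is not set up to isolate it. Moving from the main analysis to the competing-risk analysis changes the model (Cox to subdistribution) and the adjustment (overlap weights to 1:1 matching), and with the adjustment the population to which the result applies. The Abstract expects at least three LMWH users per rivaroxaban user, so 1:1 matching keeps at most one third of the LMWH patients. The sentence names only rivaroxaban and LMWH, so the DOAC-group comparison, which is an objective in section 8.1, is left out.

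At stake is whether a reader can learn the absolute risks of VTE and bleeding under each treatment, and whether competing death changes the comparison.

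**Working it through.** **Inputs (section 9.5):** 5,600 patients; mean follow-up 0.6 years; rates per person-year of 0.118 (VTE), 0.144 (bleeding) and 0.80 (death).

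**Reproducing the plan's event counts.** Person-years = 5,600 × 0.6 = 3,360.
- VTE: 3,360 × 0.118 = 396 (plan: 390)
- Bleeds: 3,360 × 0.144 = 484 (plan: 480)
- Deaths: 3,360 × 0.80 = 2,688 (plan: 2,670)

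All three agree within 3%, so the rates are used as stated.

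**Deaths per event.** VTE: 80.0/11.8 = 6.8 by rates and 2,670/390 = 6.8 by counts. Bleeding: 80.0/14.4 = 5.6 and 2,670/480 = 5.6. These are first-year figures; the protocol gives no 3-month rates.

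**Risk with death ignored and with death competing.** Assume constant hazards, event rate r, death rate d = 0.80 and time t in years.
- Death treated as ordinary censoring: 1 − exp(−rt)
- Death as competing event: r/(r+d) × [1 − exp(−(r+d)t)]

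Example, VTE at 12 months: 1 − exp(−0.118) = 11.13%, against 0.118/0.918 × [1 − exp(−0.918)] = 7.72%.

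| Horizon | VTE, death ignored | VTE, death competing | Bleeding, death ignored | Bleeding, death competing |
|---|---|---|---|---|
| 3 months | 2.91% | 2.64% | 3.54% | 3.21% |
| 6 months | 5.73% | 4.73% | 6.95% | 5.74% |
| 12 months | 11.13% | 7.72% | 13.41% | 9.32% |

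For VTE the gap is 0.27 percentage points at 3 months, 1.0 at 6 and 3.4 at 12. The plan's own count as a proportion, 390/5,600 = 7.0%, lies near the competing-risk figure.

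**Two checks on the assumptions.**
- Fatal VTE is part of the outcome (section 8.1), so not every death competes. In the extreme case where every recurrence is fatal, the competing rate falls to 0.80 − 0.118 = 0.682. The 12-month figure is then 0.118/0.80 × [1 − exp(−0.80)] = 8.1%, still well below 11.1%.
- If early mortality were 160 per 100 person-years (an assumption), the 3-month VTE risk with death competing would be 0.118/1.718 × [1 − exp(−1.718 × 0.25)] = 2.4%, a gap of about 0.5 points.

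**Effect on the comparison.** Take a cause-specific VTE HR of 0.75 (the detectable value in section 9.5) and LMWH rates as above. The approximate subdistribution HR is ln(1 − CIF, DOAC)/ln(1 − CIF, LMWH), where CIF is the risk with death competing.

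| Death HR | 3 months | 12 months |
|---|---|---|
| 0.89 (detectable value in section 9.5) | 0.758 | 0.782 |
| 0.70 (assumed) | 0.773 | 0.838 |
| 0.50 (assumed) | 0.788 | 0.903 |

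**The case against.** The strongest reply is that nothing in the main analysis is invalid. A reader might infer that the Cox HR is biased because deaths are censored. It is not: it is a proper cause-specific HR, it fits section 9.7's aim of comparing event rates, and section 9.5 sizes the study on HRs.

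A reader might also infer that the study will overstate the 12-month VTE risk by 44% (11.13/7.72 = 1.44). The documents do not support that, because no Kaplan–Meier risk is planned. The figure shows only what would happen if someone read a risk off while ignoring death.

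Nor are all primary outcomes affected. Only VTE is worded as a risk, and all-cause mortality has no competing event. At 3 months the gap is small.

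It would also go too far to say that the plan cannot separate matching from the model. Section 9.7 and the Abstract list 1:1 matching without the competing-risk model, so a matched Cox analysis is plausibly intended already. That death ends follow-up through the end of database activity is likewise an inference, since the text does not say so.

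Finally, estimators and interval methods are usually SAP material. That holds for detail, but the protocol itself has fixed the effect measure and the pairing of the competing-risk model with matching. No passage puts a competing-risk model in the overlap-weighted cohorts or covers DOACs versus LMWH. That part stands.

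**Conclusion.** The point holds for recurrent VTE and bleeding as an inexpensive improvement. The 3-month VTE risk named in section 9.3.2 is not estimated by the main analysis. The single competing-risk analysis cannot by itself show what competing death does to the main result, and it omits one of the two planned comparisons.

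The size depends on the horizon. At 3 months, ignoring death would shift a VTE risk by about 0.3 points and, with a death HR of 0.89, move an HR of 0.75 to about 0.76. At 6 and 12 months, which are secondary, or if mortality differs strongly between arms, the difference is material. These figures assume constant hazards at the section 9.5 rates, with all deaths competing. The death HRs of 0.70 and 0.50 are illustrations, as the protocol gives no mortality by arm.

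**What to change.** In the overlap-weighted cohorts, for rivaroxaban versus LMWH and for DOACs versus LMWH:
- Report weighted cumulative incidence and risk differences for VTE and bleeding at 3, 6 and 12 months, with death as the competing event and bootstrap 95% confidence intervals. Count fatal VTE or fatal bleeding as the outcome event.
- Label the Cox HR for VTE and bleeding as cause-specific, and state how death is handled in follow-up.

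Under Sensitivity analyses in section 9.7, split the combined sentence in two: (i) the subdistribution model in the overlap-weighted cohorts; (ii) 1:1 matching with the same Cox model as the main analysis, as the weighting discussion in that section already suggests.

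The cost is a few more outputs from the same data and some bootstrap computing time. No new data are needed.

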9.8 Quality control

- All coding (Read medical codes, SNOMED codes, OPCS, ICD-codes and product codes) will be prepared and reviewed by at least two clinical experts and trained investigators to assure its accuracy.
- IfESI and LIRN have developed standard definitions of recurrent venous thromboembolism [4], many variables and disease states and developed programs/coding to apply these standards as needed on projects. These standards help ensure consistency, repeatability, and accuracy for each project.
- A random sample of identified potential VTE recurrences and significant bleeding events will be manually reviewed by utilizing patient summaries/profiles including HES APC, HES Outpatient, ONS DRD and GP recorded symptoms, signs, laboratory tests, diagnostic and therapeutic procedures, medication use, discharge diagnoses, and cause of death to confirm the that both exposure (anticoagulant) and outcomes have been appropriately identified.

The external partners IfESI and LIRN will follow implemented quality assurance steps to assure a low risk of errors:

Appropriate working conditions

- Execution of workflow by adequately qualified personnel
- Foresighted planning of timelines to reduce time pressure
- Provision of a convenient working environment

Standardization of processes

- Adherence to standard operating procedure descriptions
- Usage of validated software and document templates
- Automatization of processes whenever feasible

Application of control mechanisms

- Review of all source code files and other documents by a 2nd individual (four-eyes principle)
- Run of analyses on 2 different personal computers and subsequent automated comparison of result files to assure reproducibility and system-independency of study results

Extensive documentation

- Usage of a version control system for source code files and other documents
- Bookkeeping of study progress and changes via log files
- Successive backups of study relevant files during study conduct

9.9 Limitations of the research methods

As with any secondary data source, CPRD databases have limitations. Key limitations include:

- Misclassification of exposures can negatively impact the internal validity of observational studies.
- In general, in database analyses, the absence of information is taken as an indication of absence of the condition. Missing values may occur in a small proportion for some lifestyle habits. In this case, individuals with missing values will be kept in the analysis and a separate category will be created for missing values of that variable.
- DOAC prescriptions started in-hospital or events in the immediate post-discharge period are likely to be missed in the CPRD UK databases. This might induce some exposure misclassification that we expect to be non-differential between patients prescribed OACS and those prescribed LWMH. This might introduce some bias towards the null in study estimates. While bias towards the null is generally considered as conservative in effectiveness analyses, it is considered as anticonservative in safety analyses (tends to conclude treatment strategies are similar even if they are not). This will be taken into account when interpreting study results.
- In database analyses where randomization is not possible, such PS based methods such as weighting or matching serve to harmonize comparison groups with respect to patient characteristics. However, residual confounding caused by e.g. unmeasured factors, missing data, miscoding or tactical coding issues, etc. may be present.

Reference Number: RD-SOP-1214
Supplement Version: 7

- CPRD captures prescriptions recorded by the PCP, but do not capture if a patient filled their prescription and/or took it. The study is thus designed as an intention-to-treat approach, subsequent recording of anticoagulants will be evaluated to estimate time on anticoagulation treatment and discontinuation rates as exploratory outcomes.
- No adjustment for multiplicity hypothesis testing will be performed.

9.10 Other aspects

None.

10. Protection of human subjects

The study will be conducted in accordance with Good Pharmacoepidemiology Practices [17]. In this investigation we will use a medical record linkage database where the information of patients is anonymized and there is no need to obtain informed consent from patients. The study protocol is dependent on approval by the independent review of CPRD's Research Data Governance (RDG) process. CPRD protects the confidentiality of patient data implementing the following processes, as listed in their webpage [18]:

- *CPRD has ethics approval from the Health Research Authority to support research using anonymised patient data*
- *CPRD must complete an annual NHS Data Security and Protection Toolkit assessment to demonstrate that it meets the required standard for holding data securely*
- *Once CPRD receives anonymised data from a GP practice, we ensure the data is fully compliant with the Information Commissioner's Office (ICO) anonymisation code of practice and that patient privacy is protected*
- *The identity of GP practices that have contributed data is concealed*
- *The data CPRD holds can only be used for public health research*
- *Only bona fide researchers can receive the data*
- *Checks are conducted on organisations carrying out and funding the research to assess whether they are suitable to receive CPRD data*

- *Requests by researchers to access the data are reviewed via the CPRD RDG Process to ensure the research benefits public health*
- *Researchers must adhere to robust terms and conditions governing how the anonymised data is used.*

11. Management and reporting of adverse events/adverse reactions

As per the EMA Guideline on Good Pharmacovigilance Practices, non-interventional study designs that are based on secondary use of data do not require individual reporting of adverse reactions. Reports of adverse events/reactions will be summarized in the study report, where applicable.

12. Plans for disseminating and communicating study results

The results of this study are intended to be published in a peer-reviewed journal and as abstracts/ presentations at medical congresses (congresses/journals to be selected following consultation with Bayer AG) and will follow the International Committee of Medical Journal Editors guidelines.

